# **3. OBJECTIVES AND ENDPOINTS**

The overall objective of the study is to determine the safety and optimal infectious dose of recombinant H3N2 (A/Texas/71/2017 (H3N2), clade 3C3a) influenza challenge virus.

OBJECTIVES	ENDPOINTS
	(OUTCOME MEASURES)
Primary	
1. To determine the optimal infectious dose  of a recombinant influenza virus (A/Texas/71/2017 (H3N2), clade 3C3a) to be used as a clinical challenge strain in future vaccine efficacy or intervention studies as assessed by viral shedding and clinical symptoms	a. Percentage of subjects within a challenge dose group with detectable shedding in nasopharyngeal (NP) swab(s) by RT-PCR  over any 2 days beginning 24 hours post challenge through Day 8 and with symptom scores that meet the clinical case definition for symptomatic infection (Modified Jackson score). See section 4.1 for the clinical case definition for symptomatic infection.
2. To describe viral detection by quantitative and qualitative RT-PCR from study subjects at baseline and post-challenge	
 
a. Percentage of subjects within a challenge dose group with detected viral shedding in NP swab(s) each day post-challenge from Day 2 through Day 8 using qualitative RT-PCR and quantitative RT-PCR
 
b. Magnitude of virus shedding post-challenge in each subject defined as the peak viral load in NP swab(s) from day 2 through Day 8 post-challenge by quantitative RT-PCR
 
c. Duration of viral shedding defined as the number of days from first positive RT-PCR to last positive RT- PCR where virus is detected in NP swab(s) by quantitative or qualitative RT-PCR post challenge day 1 for each subject
 

3. To document clinical symptoms from self- reported surveys and standardized symptom scales at baseline and post challenge	
 
a. Computed total symptom score from modified Jackson score through Day 8 and at Day 15.
 
b. Percentage of subjects with total symptom scores that define symptomatic or asymptomatic categories based on modified Jackson score for each subject
 

Secondary	

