3. STUDY OBJECTIVES AND ENDPOINTS

3.1. Study Objectives and Endpoints

The study objectives and endpoints addressed in this SAP are presented below. The remaining exploratory objectives not included this SAP will be addressed in addenda to this analysis plan.

OBJECTIVES	ENDPOINTS (OUTCOME MEASURES)
Primary	
1. To determine the optimal infectious dose ¹ of a recombinant influenza virus (A/Texas/71/2017 (H3N2), clade 3C3a) to be used as a clinical challenge strain in future vaccine efficacy or intervention studies as assessed by viral shedding and clinical symptoms	a. Percentage of participants within a challenge dose group with detectable shedding in nasopharyngeal (NP) swab(s) by RT-PCR over any 2 days beginning 24 hours post challenge through Day 8 and with symptom scores that meet the clinical case definition for symptomatic infection (Modified Jackson score). See Section 3.2 for the clinical case definition for symptomatic infection.
2. To describe viral detection by quantitative and qualitative RT-PCR from study participants at baseline and post-challenge	a. Percentage of participants within a challenge dose group with detected viral shedding in NP swab(s) each day post-challenge from Day 2 through Day 8 using qualitative RT-PCR and quantitative RT-PCR b. Magnitude of virus shedding post-challenge in each participant defined as the peak viral load in NP swab(s) from day 2 through Day 8 post-challenge by quantitative RT-PCR c. Duration of viral shedding defined as the number of days from first positive RT-PCR to last positive RT-PCR where virus is detected in NP swab(s) by quantitative or qualitative RT-PCR post challenge day 1 for each participant
3. To document clinical symptoms from self-reported surveys and standardized symptom scales at baseline and post challenge	a. Computed total symptom score from modified Jackson score through Day 8 and at Day 15. b. Percentage of participants with total symptom scores that define symptomatic or asymptomatic categories based on modified Jackson score for each participant

OBJECTIVES	ENDPOINTS (OUTCOME MEASURES)
Secondary	

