3.2.2. Viral Shedding Status and Duration of Viral Shedding

Viral shedding status will be determined for each participant on each study day during the challenge period, classified as follows:

- **RT-PCR+** if a qualitative RT-PCR result from the Biofire or Luminex multiplex assay is reported to be positive for Influenza A or Influenza A H3, and/or if a quantitative RT-PCR is reported to have detectable H3N2 virus.
- **RT-PCR-** if the qualitative RT-PCR results for Influenza A and Influenza A H3 are negative and the quantitative RT-PCR result indicates undetectable quantities of virus.

Detectable virus for the quantitative RT-PCR assay will be defined as being any quantity above a lower limit of detection (LLOD) reported by the laboratory conducting the assay.

Duration of viral shedding will be defined as time from the initial positive NP swab until the day after the final positive NP swab, with positivity defined as above. Intermittent negative results will be ignored for this computation.

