3.2.4. Peak and Total Viral Shedding

Viral copies/mL will be estimated as a mean across quantitative RT-PCR replicates. Some replicates may be dropped from the calculations if potential quality control issues are noted. Values below the lower limit of detection will first be imputed as LOD/2 prior to taking the mean of the replicates.

Peak viral shedding will be calculated as the maximum viral concentration (RNA copies/mL) recorded the duration of the inpatient study period for each individual.

Total viral shedding over the inpatient period will be summarized by the area under the curve (AUC), approximated via the linear trapezoidal method, where the trajectory of an individual's viral concentration is

partitioned into $n-1$ subareas until the last inpatient observation at time t_n . As the linear trapezoidal AUC method approximates the entire area by calculating the cumulative sum of the subareas, the formula that will be applied is:

$$AUC_i = \frac{1}{2} * \sum_{j=1}^{n-1} (t_{j+1} - t_j) * (C_{ij+1} + C_{ij})$$

where $(t_{j+1} - t_j)$ is the difference between the j th and $j+1$ th time points within the inpatient period, and C_{ij} and C_{ij+1} are the viral concentrations measured at the j th and $j+1$ th time points for the i th individual. Intermittent missing values are expected to be minimal, so no imputation is planned.

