7.1.3. Viral Shedding – Timing, Duration, and Magnitude

Viral shedding is measured by qualitative and quantitative RT-PCR, which are both incorporated into determining viral shedding status (binary yes/no) for a given day, as described in [Section 3.2.2](#).

Qualitative RT-PCR status will be cross-tabulated with RT-qPCR status (RT-PCR+/undetectable) by challenge dose group in [Table 28](#). Qualitative RT-PCR results will be summarized for all targets of the multiplex assays for each study day during the challenge period in [Table 29](#) through [Table 32](#). An overall comparison of qualitative and quantitative RT-PCR results will be presented in [Table 33](#), to assess the agreement of the two assays.

The number of days to first detected viral shedding will be summarized by challenge dose group in [Table 34](#). The median number of days to infection and corresponding 95% CI will be estimated for each group via the Kaplan-Meier method, in order to account for the censoring of participants who never tested RT-PCR+ throughout the challenge period.

The number of total days with RT-PCR+ results will be summarized by challenge dose group in [Table 35](#). A summary of peak viral shedding, total viral shedding (via AUC), and the duration of viral shedding (from first positive through last positive) will be presented in [Table 36](#).

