8. IMMUNOLOGICAL EVALUATION

8.1. Secondary Immunogenicity Analyses

Only secondary immunogenicity analysis of HAI, MN, NAI, and anti-HA stalk assay data will be included in the interim CSR. Exploratory immunogenicity analysis not included in this SAP will be planned in a separate SAP addendum to this analysis plan and presented in an addendum to the CSR or one or more separate reports for the purposes of manuscript development.

Immunogenicity analyses are planned in the ITT population. If 10% or more of the timepoints utilized in the immunogenicity analyses would be excluded by the list given in [Section 5.3.3](#) to define the Per Protocol population, the secondary immunogenicity analyses will be conducted in the PP population as a sensitivity analysis.

HAI, MN, and anti-HA stalk antibody titers against the challenge strain will be analyzed by time point, challenge dose group, and infection status in [Table 49](#), [Table 50](#), and [Table 52](#), respectively. Geometric mean titers (GMTs) will be computed at each time point for each group, as well as geometric mean fold-rise (GMFR) and seroconversion (as defined in [Section 3.2.7](#)) at each post-challenge time point. Associated 95% CIs will be presented as well. GMTs and 95% CIs will be presented graphically in [Figure 16](#) and [Figure 18](#), and the entire distribution of titers reported at each visit will be presented in reverse cumulative distribution (RCD) curves in [Figure 19](#), [Figure 20](#), and [Figure 22](#).

The assays will be analyzed similarly by symptomatic infection status in [Table 53](#), [Table 54](#), and [Table 56](#).

Antibody titers will be listed, by assay, in [Listing 11](#).

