2	x	x.x	x	x.x	x	x.x	x	x.x
3-6	x	x.x	x	x.x	x	x.x	x	x.x
7+	x	x.x	x	x.x	x	x.x	x	x.x

Notes: N = Number of participants in the Safety population; n = Number of participants reporting a given number of days of positive qualitative and/or quantitative RT-PCR results.

Table 36: Summary of Peak, Total, and Duration of Viral Shedding by Challenge Dose Group, Safety Population*

Variable	Statistic	10 ⁴ TCID ₅₀ Challenge Virus (N=X)	10 ⁵ TCID ₅₀ Challenge Virus (N=X)	10 ⁶ TCID ₅₀ Challenge Virus (N=X)	Sham Inoculum (N=X)
Peak viral load (log-10 copies/mL)	Mean (95% CI)	x.x (x.x, x.x)	x.x (x.x, x.x)	x.x (x.x, x.x)	x.x (x.x, x.x)
	Standard Deviation	x.x	x.x	x.x	x.x
	Minimum	x.x	x.x	x.x	x.x
	Median	x.x	x.x	x.x	x.x
	Maximum	x.x	x.x	x.x	x.x
AUC (log-10 copies/mL) ^a	Mean (95% CI)	x.x (x.x, x.x)	x.x (x.x, x.x)	x.x (x.x, x.x)	x.x (x.x, x.x)
	Standard Deviation	x.x	x.x	x.x	x.x
	Minimum	x.x	x.x	x.x	x.x
	Median	x.x	x.x	x.x	x.x
	Maximum	x.x	x.x	x.x	x.x
Duration of Viral Shedding ^b	Mean (95% CI)	x.x (x.x, x.x)	x.x (x.x, x.x)	x.x (x.x, x.x)	x.x (x.x, x.x)
	Standard Deviation	x.x	x.x	x.x	x.x
	Minimum	x.x	x.x	x.x	x.x
	Median	x.x	x.x	x.x	x.x
	Maximum	x.x	x.x	x.x	x.x

Note: N = Number of participants in the Safety population followed for the entire challenge period.

^aArea under the curve calculated using raw viral copies/mL through discharge from the challenge unit, then log-10 transformed.

^bDuration measured as the number of days between the first positive and last negative RT-PCR results, inclusive, regardless of any intermittent negative results.

Table 37: Maximum Severity of Participant-Reported FLU-PRO Symptoms by Study Day, 10⁴ TCID₅₀ Challenge Virus Group, Currently Infected Participants in the Safety Population

		Baseline (N=XX)		Day 1 (Post-Challenge) (N=XX)		Day 2: RT-PCR+ (N=XX)		Day 3: RT-PCR+ (N=XX)		Day 4: RT-PCR+ (N=XX)		Day 5: RT-PCR+ (N=XX)		Day 6: RT-PCR+ (N=XX)		Day 7: RT-PCR+ (N=XX)		Day 8: RT-PCR+ (N=XX)		Days 9+: RT-PCR+ (N=XX)		Anytime Post-Challenge ^a : RT-PCR+	
Symptom	Extent	n	%	n	%	n	%	n	%	n	%	n	%	n	%	n	%	n	%	n	%	n	%
Any Symptom	0	x	x.x	x	x.x	x	x.x	x	x.x	x	x.x	x	x.x	x	x.x	x	x.x	x	x.x	x	x.x	x	x.x
	1	x	x.x	x	x.x	x	x.x	x	x.x	x	x.x	x	x.x	x	x.x	x	x.x	x	x.x	x	x.x	x	x.x
	2	x	x.x	x	x.x	x	x.x	x	x.x	x	x.x	x	x.x	x	x.x	x	x.x	x	x.x	x	x.x	x	x.x
	3	x	x.x	x	x.x	x	x.x	x	x.x	x	x.x	x	x.x	x	x.x	x	x.x	x	x.x	x	x.x	x	x.x
	4	x	x.x	x	x.x	x	x.x	x	x.x	x	x.x	x	x.x	x	x.x	x	x.x	x	x.x	x	x.x	x	x.x
Nose																							

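### Table 36 pools infected and never-infected participants, so its dose-group means for peak load and AUC cannot show how much infected participants shed

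*SAP*

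**What the plan says.** Protocol section 3 defines primary endpoint 2b thus: "Magnitude of virus shedding post-challenge in each subject defined as the peak viral load in NP swab(s) from day 2 through Day 8", by quantitative RT-PCR. SAP 3.1 repeats it with participants in place of subjects. Endpoint 2c is the duration of shedding.

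SAP 7.1.3 makes Table 36 the place of reporting: "A summary of peak viral shedding, total viral shedding (via AUC), and the duration of viral shedding (from first positive through last positive) will be" (the sentence goes on to name that table). The shell has four columns (three doses and sham). Each measure gets a mean with 95% CI, SD, minimum, median and maximum. There is no infected-only row and no n row, and the population note is "N = Number of participants in the Safety population followed for the entire challenge period". The asterisk in its title places the table in the topline report described in SAP 5.2.

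The derivations are in SAP 3.2.4. On non-detects: "Values below the lower limit of detection will first be imputed as LOD/2 prior to taking the mean of the replicates". On peak: "Peak viral shedding will be calculated as the maximum viral concentration (RNA copies/mL) recorded the duration of the inpatient study period for each individual". A footnote to Table 36 adds that AUC is computed on raw copies and then log-transformed. For duration, SAP 3.2.2 says: "Duration of viral shedding will be defined as time from the initial positive NP swab until the day after the final positive NP swab". No value is given for someone who is never positive.

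Other outputs do split by infection status. Table 34 has a row for infected participants, Table 43 has infected and uninfected columns, and SAP 8.1 says antibody titers "will be analyzed by time point, challenge dose group, and infection status in" Tables 49, 50 and 52.

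**The concern.** A participant with no detectable virus on any day has a peak of LOD/2 and an AUC of LOD/2 times the length of observation. Within a dose group, the mean log10 peak is then a weighted average of two quantities: the load in those who shed, and an assay constant in those who did not. The weight is the share with detectable virus, which rises with dose if the challenge behaves as the protocol expects.

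SAP 2.1 lists describing shedding after infection among the study's goals. A later vaccine study that uses reduced shedding as an outcome needs the level and spread of shedding in infected people at the chosen dose. If the only dose-level summary is the composite, a reader of the topline report may take a difference in infection rate for a difference in shedding intensity, or may miss a real one.

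**Working it through.** **The plan's own figures.** Neither document gives an LOD, expected load, SD or precision for peak, AUC or duration, so there is no planned figure to reproduce. The nearest figures concern event counts, and they reproduce. The exact 95% interval for 15/30 is (31.3%, 68.7%), as stated. The chance of at least 8 events in 10 is 0.012 at a true probability of 0.4 and 0.678 at 0.8, against 0.01 and 0.67 in protocol 9.3.2.

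**Inputs.**
- Shares with detectable virus: 40% and 80% are borrowed from that protocol illustration, and 55% and 80% from the target attack-rate range in SAP section 2. 60% is added as a smaller contrast. The documents use the borrowed figures for the decision endpoint, so applying them to detectable virus is an assumption.
- LOD: assumed 10^2 to 10^3 copies/mL.
- Mean infected log10 peak: assumed 5 to 7, the same at both doses.

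**Peak.** With share p, infected mean m and floor f = log10(LOD/2), the pooled mean is p·m + (1 − p)·f. With identical infected shedding, two doses differ by (p2 − p1)·(m − f).

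Worked case, LOD 500 and m = 6, so f = log10(250) = 2.40:
- 40%: 0.4 × 6 + 0.6 × 2.40 = 3.84
- 80%: 0.8 × 6 + 0.2 × 2.40 = 5.28
- Difference: 0.4 × 3.60 = 1.44 log10, with none among infected participants.

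| LOD | m | f | m − f | 40% v 80% | 55% v 80% | 40% v 60% |
|---|---|---|---|---|---|---|
| 1000 | 5 | 2.70 | 2.30 | 0.92 | 0.58 | 0.46 |
| 500 | 6 | 2.40 | 3.60 | 1.44 | 0.90 | 0.72 |
| 100 | 7 | 1.70 | 5.30 | 2.12 | 1.33 | 1.06 |

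The first and last rows are the extremes of the assumed grid. The median does not avoid the problem: when fewer than half of a group are detectable, it sits on the floor.

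**Masking.** The pooled means at 40% and 80% are equal when the infected mean at the higher dose is lower by (m − f)·(1 − 0.4/0.8). That is 1.15, 1.80 and 2.65 log10 for the three rows above.

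**AUC.** The same mixture applies. Over Days 2 to 8 (six days), a never-detectable participant has log10(6 × LOD/2): 2.48, 3.18 and 3.48 for an LOD of 100, 500 and 1000.

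**Duration.** LOD/2 plays no part here. Assume infected participants average 5 days. If never-positive participants are coded zero, the means are 0.4 × 5 = 2.0 and 0.8 × 5 = 4.0 days. If they are treated as missing, both means are 5 days. The SAP does not say which applies.

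**Can the infected-only figure be found elsewhere?**
- Table 28 gives, by dose, the number ever positive by quantitative RT-PCR. With Table 36 this allows (pooled mean − (1 − p)·f)/p; in the worked case (3.84 − 1.44)/0.4 = 6.0. The denominators differ (participants with available results, against those followed throughout), and no SD or CI results.
- Table 33 pools samples across doses.
- Table 35 bands the number of positive days by dose, which partly covers duration.
- Figure 12 plots individual AUC against symptom scores, with no summary by dose and infection status.
- None of the 22 listings in SAP Appendix 3 covers viral load.

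**The case against.** The strongest reply is that Table 36 does what the endpoint says. Endpoint 2b is defined for each participant, and protocol 9.5.2 plans means for each group without restriction to infected subjects. Averaging over everyone challenged avoids conditioning on a post-challenge event. If a dose infects more people, higher mean shedding among those challenged is real. All of this stands. A reader might infer that the all-participant rows are wrong or should be demoted; the documents do not support that.

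A reader might also infer that a more infectious dose must always appear to shed more and longer, or that the table merely repeats the infection rate. Neither follows. For peak and AUC, both hold only when infected loads are similar across doses, and the masking result shows the opposite can occur. For duration, SAP 5.1 bases summaries on non-missing data, so never-positive participants may simply drop out, and then there is no dilution.

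No design decision depends on the table. The optimal dose is chosen on attack rate and safety (protocol 9.5.2), Table 36 has no p-value column, and SAP 5.8 calls the analysis mainly descriptive. For that reason no test error rate is claimed here, although protocol 9.5.2 does plan group comparisons of these means. SAP 5.1 allows bootstrap intervals if the t-distribution is unsuitable, but that changes the interval and not the quantity being estimated. SAP 5.3 permits analyses in infected subsets but assigns none to this table.

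**Conclusion.** The point holds as a gap in reporting. Table 36 gives a legitimate all-challenged summary of peak and AUC, but that summary mixes incidence with magnitude, and nothing else planned gives magnitude by dose among infected participants with a measure of spread. A dose difference in Table 36 therefore cannot be read as a difference in shedding by infected people, and a null difference cannot be read as its absence.

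Under identical infected shedding, the difference attributable to infection rate alone is about 0.9 to 2.1 log10 at 40% versus 80%, 0.6 to 1.3 at 55% versus 80%, and 0.5 to 1.1 at 40% versus 60%. These sizes rest wholly on assumed LODs and loads; the direction of the argument does not. For duration, the established defect is only that the coding of never-positive participants is unstated.

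**What to change.** Amend the Table 36 shell and SAP 7.1.3:

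- Add rows, by dose group and with n, for infected participants (RT-PCR positive on at least two days, SAP 3.2.3) for peak, AUC and duration.
- Keep the all-participant peak and AUC rows, labelled as combining incidence and magnitude.
- Outside the infected-only rows, summarise duration only in participants with a positive result, with n.
- Label the infected-only rows descriptive, because the subset is defined after challenge.
- Footnote that infected participants positive only by the qualitative assay still carry floor values. Participants positive on a single day count as uninfected under SAP 3.2.3 but may have a measured load.

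In the same edit, reconcile the end point of duration: the Table 36 footnote runs to the last negative result, SAP 3.2.2 to the day after the final positive, and SAP 7.1.3 through the last positive.

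The cost is SAP wording and a few rows from data already derived. The downside is smaller n and wider intervals in the infected-only rows, most noticeably in a dose group of about 10.

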Viral shedding will be summarized by the number and percentage of subjects in each challenge dose group with positive qualitative and/or quantitative RT-PCR each day from Day 2 through the end of the challenge period (Day 8 or later, in the case of a subject not meeting discharge criteria on Day 8) excluding safety results reported after receipt of antiviral therapy. The probability of viral shedding at any point during the challenge (i.e., incidence) will be estimated along with the associated exact 95% CI, separately by challenge dose group. Peak viral shedding will be calculated for each subject as the maximum shedding from Day 2 through Day 8 or discharge, and total viral shedding will be calculated via the area under the curve (AUC) with study day on the x-axis and shedding on the y-axis. These will be calculated separately for quantitative RT-PCR and quantitative culture. Mean peak and total shedding based on the AUC will be calculated for each group along with 95% CIs, and comparisons will be made as described for continuous variables in Section 9.5.1. A Wilcoxon signed-rank test will be used to compare distributions of these variables between quantitative RT-PCR and quantitative culture across all subjects, to assess if these methods of viral quantification are consistent. Scatterplots will also be presented, along with Spearman rank-order correlation estimates. Duration of viral shedding will be calculated for each subject as the number of days (including non-consecutive) determined by qualitative or quantitative RT-PCR to be positive from Day 2 until discharge; means and 95% CIs will be calculated for each group and comparisons will be made.

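### Duration of viral shedding, a primary endpoint, is stated in three conflicting ways, and the Table 36 footnote, programmed as written, runs to the last negative swab instead of the last positive

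*SAP*

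**What the plan says.** Three quantities carry the same name.

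- **Span from first to last positive.** Protocol Section 3 has the "number of days from first positive RT-PCR to last positive" result, and SAP 3.1 repeats it. SAP 3.2.2 gives the derivation: "Duration of viral shedding will be defined as time from the initial positive NP swab until the day after the final positive NP swab", with negatives in between ignored. SAP 7.1.3, which sends the reader to Table 36, describes the "duration of viral shedding (from first positive through last positive" result).
- **Count of positive days.** Protocol 9.5.2 calculates duration as "the number of days (including non-consecutive) determined by qualitative or quantitative RT-PCR to be positive from Day 2 until discharge". The SAP shows this count separately, in Table 35.
- **First positive to last negative.** SAP Table 36, footnote b, has the "number of days between the first positive and last negative RT-PCR results, inclusive", regardless of intermittent negatives.

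Table 36 is asterisked as a topline table. SAP 5.2 says topline results are final and go into the clinical study report, and that a portion of the topline analyses will be presented at a 2023 network meeting. SAP Section 14 declares no substantive change from the protocol's planned analysis.

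**The concern.** The footnote contradicts both the SAP text that calls the table and the SAP's own derivation. A programmer working from the table shell would end the interval at the wrong swab. Because participants keep being swabbed after they clear the virus and leave only after negative tests, the last negative result is normally the final swab before discharge. The row would then mostly reflect when a participant first turned positive and when the unit discharged them, not when shedding stopped.

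There is also a conflict between the documents that correcting the footnote would not settle. The protocol's count and the SAP's span differ whenever a negative falls between positives. SAP 3.2.1 openly flags its one change to the case definition, but nothing flags the move from count to span.

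**Working it through.** The documents give no numerical duration to reproduce, so the check applies each rule literally to swab patterns. The patterns are illustrative.

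**Inputs**
- Daily swabs on Days 2 to 8, and longer if still positive (SAP 4.6.1).
- Stay of at least seven days after challenge, that is, to Study Day 8 (Schedule of Activities, note 7).
- Discharge needs two consecutive negative qualitative tests 12 hours apart, from Day 6 on (same note).
- A day is positive if either the qualitative or the quantitative assay is positive (SAP 3.2.2).

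**Formulas**, with F = first positive day, L = last positive day, N = last negative day:
- Endpoint tables: L − F if read as elapsed days, L − F + 1 if read inclusively
- SAP 3.2.2: (L + 1) − F
- Protocol 9.5.2: number of positive days
- Table 36, footnote b: N − F + 1

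The inclusive span and SAP 3.2.2 are algebraically the same.

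| Positive days (other days negative) | Last swab | Elapsed span | Inclusive span = SAP 3.2.2 | Count | Footnote b |
|---|---|---|---|---|---|
| 2 | Day 8 | 0 | 1 | 1 | 7 |
| 2–3 | Day 8 | 1 | 2 | 2 | 7 |
| 2–6 | Day 8 | 4 | 5 | 5 | 7 |
| 2, 3, 6 | Day 8 | 4 | 5 | 3 | 7 |
| 5–6 | Day 8 | 1 | 2 | 2 | 4 |
| 3–8 | Day 10 | 5 | 6 | 6 | 8 |
| 2–8 (quantitative assay still positive at discharge) | Day 8 | 6 | 7 | 7 | undefined: no negative from Day 2 on |
| 3–8 (as above, Day 2 negative) | Day 8 | 5 | 6 | 6 | 2 − 3 + 1 = 0 |

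**General result for Day 8 discharge.** If the Day 8 swab is negative, N = 8 and footnote b gives 8 − F + 1 = 9 − F, with L absent. There are 2^6 − 1 = 63 patterns with at least one positive on Days 2 to 7 and a negative Day 8. The identity held in all 63, as did equality of the inclusive span and SAP 3.2.2. With F = 2, footnote b is 7 for every L from 2 to 7, while the inclusive span runs from 1 to 6. The upper end is 5 if the two discharge negatives fall on separate days and both assays agree.

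**Size of the error.** Footnote b minus the inclusive span is N − L. For Day 8 discharges this is 8 − L, so the inflation is largest for those who clear soonest. Rankings can reverse: positive on Day 2 only scores 9 − 2 = 7 (true 1), while positive on Days 4 to 6 scores 9 − 4 = 5 (true 6 − 4 + 1 = 3).

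**Later discharge.** Positive on Days 3 to 8 and negative on Days 9 and 10 scores 10 − 3 + 1 = 8 (true 6). Late clearance still lengthens the measure.

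**The case against.** The best defence is that the footnote is a drafting slip. SAP 7.1.3 states what Table 36 contains, SAP 3.2.2 defines the variable correctly, and the footnote's clause about intermittent negatives makes sense only for an interval ending at a positive. The appendix shells have other copying errors: Table 60 labels three dose columns 10^4, and Table 43 explains titre abbreviations under symptom scores. Daily positivity, total positive days, peak and AUC are all reported elsewhere. A careful programmer might well follow the SAP body.

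Most of this stands. The slip is the likeliest explanation, and the SAP body holds the right rule. But the footnote specifies a topline row for a primary endpoint, and the SAP has no rule that text overrides a shell. The defence also leaves the count in Protocol 9.5.2 unreconciled.

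A reader might infer that there are four definitions. That requires the endpoint tables to mean elapsed days; read inclusively, they agree with SAP 3.2.2 and three quantities remain. A reader might also call the footnote version time to discharge. It starts at first positive, not at challenge, and it need not end at the discharge swab, because discharge uses the qualitative assay alone while SAP status uses both.

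**Conclusion.** The point holds. Three conflicting quantities carry one primary-endpoint name, and the Table 36 version would report the wrong one if programmed as written. For participants with a negative Day 8 swab on combined status and Day 8 discharge, it depends only on the first-positive day, which Table 34 already summarizes. Its excess over the true span is 8 − L days. For participants still positive by the quantitative assay at discharge it can be undefined or non-positive.

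A reader might go further and infer that the measure says nothing about clearance and cannot separate dose groups. The documents do not support that. Participants who remain positive stay longer and score longer, and the measure varies with first-positive day. It is biased upward, and the clearance information is lost for Day 8 discharges only.

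Nor does this threaten the trial's main conclusion. Dose escalation and selection of the optimal dose rest on the attack rate and safety (Protocol 9.5.2 and 9.5.6.2), and the SAP analysis is mainly descriptive. It should be fixed before the topline table is programmed. The conclusion assumes the scheduled daily swabs and the stated discharge rule; how many participants fall in each pattern is not known from the documents.

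**What to change.** 1. In Table 36, change footnote b so that the interval ends at the last positive result: last positive day minus first positive day plus 1, which equals SAP 3.2.2.
2. In SAP 3.2.2, state that both end days count, and say how never-positive and sham participants enter the Table 36 summary (scored zero, or left out with their number shown). No current text settles this, although the table has a sham column and a denominator of everyone followed through the challenge period. Either choice is workable; restricting to ever-positive participants is a preference, not something the documents require. Row 0 of Table 35 already gives the never-positive number.
3. In SAP Section 14, record that the span replaces the count in Protocol 9.5.2 and that the count remains in Table 35.

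The cost is one footnote, one or two sentences in SAP 3.2.2 and one entry in Section 14. It needs no new data and no new analysis, and recording the departure in the SAP avoids rewording the protocol.
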